7.2.5. Reporting Urgent Safety Measures

If any urgent safety measure is taken the research team should inform the Sponsor with 24 hours using the Sponsors safety incident reporting form. The Sponsor will inform the REC and participating sites of the measures taken and the circumstances giving rise to those measures within 3 days on implementation of the urgent safety measure.

8. DATA HANDLING

8.1. Data Collection Tools

Study data will be entered at site into electronic case report forms (eCRF) directly by study personnel. The study will use an electronic data capture (EDC) system to store all data securely. The database will be a cloud-based EDC hosted by a fully validated 3rd party vendor. The database will be compliant with ICH-GCP and MHRA guidelines for computerised systems. Derby CTSU will be responsible for database design, build and data validation while the provider of the software will be responsible for hosting and storage of the study data. Access to the EDC will be assigned based on study roles.

After data entry is performed, validation checks will be applied to the data to ensure accuracy and consistency according to the data validation plan. All data queries generated as a result of these checks will be available online for resolution by the site. Processing of study data and monitoring for consistency, validity and quality will be undertaken by study statisticians, data and trial manager on an

ongoing basis during recruitment. After data entry is complete and all data queries have been resolved, the database will be locked and released for statistical analysis.

Participants will be identified only by their unique study number assigned by the Electronic Data Capture system. The NHS numbers will be linked to the study numbers and this information will be stored securely locally at each hospital with restricted access.

Participant reported outcomes will be captured via a series of participant questionnaires (outlined in Section 3.2). Paper questionnaires will be issued to participants at the required time points by site staff in clinic or posted to the participants. Participants will complete their responses within the questionnaire booklet, and return the completed document to site, for entry onto the trial database.

8.2. Source Data

Source documents are where data are first recorded, and from which participants' CRF data are obtained. These include, but are not limited to, hospital records (from which medical history and previous and concomitant medication may be summarised into the eCRF), and correspondence.

Outcome	Source		
Participant Demographics	Patient case records		
Medical History	Patient case records		
Indication for Surgery	Patient case records		
Operative Details	Operation notes		
Post-Surgery Histology	Histology report		
Post-Surgery Treatment	Patient case records		
Details			
Questionnaires (Breast Q,	Paper or scanned		
EQ-5D-5L)	questionnaires		

eCRF entries will be considered source data if the CRF is the site of the original recording (e.g. there is no other written or electronic record of data). All documents will be stored safely in confidential conditions. On all trial-specific documents, other than the signed consent, the participant will be referred to by the trial participant number, not by name.

Investigators should keep records of all participating patients and all original signed informed consent forms. It is necessary for investigators to provide access to source document for monitoring and audit purposes to Sponsor, any monitoring or regulatory authorities as deemed necessary.

8.3. Data handling and reporting

Data will be collected and retained in accordance with the Caldicott Principles, UK Data Protection Act 2018 and General Data Protection Regulation (GDPR).

8.4. Access to Data

Direct access will be granted to authorised representatives from the Sponsor, host institution and the regulatory authorities to permit study-related monitoring, audits and inspections.

8.5. Archiving

At the end of the study, following completion of the end of study report, UHDB will securely archive all centrally held study related documentation for a minimum of 10 years. At the end of the defined archive period arrangements for confidential destruction will be made. It is the responsibility of each PI to ensure

that data and all essential documents relating to the study are retained securely for a minimum of 10 years after the end of study, and in accordance with national legislation. All archived documents must continue to be available for inspection by appropriate authorities upon request.

9. STATISTICS AND DATA ANALYSIS

9.1. Sample Size Calculation

The sample size is 60. Sample sizes between 30 and 50 are recommended for a feasibility study[16, 17]. By recruiting 60 (out of 120) we will be able to estimate a participation rate of 50% of women offered the trial to within a 95% confidence interval of +/-9% and a completion rate of 90% (54 of 60) within a 95% confidence interval of (80%, 95%).

9.2. Statistical Analysis

Descriptive statistics will be presented to summarize the distribution of demographic and baseline variables across each of the randomisation groups. A Consolidated Standards of Reporting Trials (CONSORT) flow diagram will be produced, showing the frequency of patients/ participants:

- · Assessed for eligibility and reasons for not eligible,
- · Approached and reasons for not approached
- · Confirmed as eligible
- Consented and reasons for not consented
- Excluded before randomisation (and the frequency of each reason for exclusion),
- Randomised,
- · Allocated to each randomisation group,
- That received each allocated type of mesh,
- That did not receive each allocated type of mesh,
- Lost to follow-up (and the frequency of each reason for loss to follow-up) for each randomisation group.
- Analysed for each randomisation group.
- Not analysed (and the frequency of each reason for not being analysed) for each randomisation group.

Primary analysis will be intention-to-treat. Clinician acceptance (proportion of eligible women offered the trial), patient acceptance (proportion of women offered the trial who participate in the trial), randomisation rate and recruitment rate (average per year) will be presented overall as proportions along with 95% confidence intervals. Compliance with allocated type of mesh and completeness of data (primary and secondary endpoints) will be presented overall and by study group using summary statistics along with 95% confidence intervals.

Secondary outcome measures will be presented overall and by study groups, as summary statistics at each assessment point. The standard deviation and effect size of Breast Q will be estimated using an Independent T-Test. Safety outcomes (AEs, SAEs, complications) will be presented with summary statistics by the treatment that has been received.

Missing data will be excluded from analysis and will not be imputed.

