3. AIMS, OBJECTIVES AND OUTCOME MEASURES/ ENDPOINTS

3.1. Objectives

To assess patient and clinician acceptance, recruitment rate, and compliance with randomly allocated type of mesh. We will explore views of women and healthcare professionals about the study; evaluate appropriateness and completeness of data on proposed future main study outcomes. The standard deviation (SD) of patient reported 'satisfaction with breasts' score on Breast Q questionnaire will inform sample size calculations for the main study.

Feasibility study will assess:

- Clinician acceptance: Proportion of eligible women offered the trial
- Patient acceptance: Proportion of women offered the trial who participate in the trial
- Recruitment rate (average per year)
- Completeness of data on proposed definitive trial study outcomes
- Compliance with allocated type of mesh

The follow-on main study will assess long-term (5 years) patient reported 'satisfaction with breasts' measured using Breast Q questionnaire, quality of life measured using Breast Q and EQ-5D-5L questionnaires, complications and economic evaluation.

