3.2. Outcomes

3.2.1. Feasibility study primary outcomes:

- Clinician acceptance: Proportion of eligible women offered the trial
- Patient acceptance: Proportion of women offered the trial who consent & are randomised in the trial
- Recruitment rate (average per year)
- Compliance with allocated type of mesh
- Completeness of data on proposed definitive trial study outcomes

3.2.2. Feasibility study secondary outcomes:

- Sample size estimation: Estimate the sample size for the main study.
- Completeness of data on proposed definitive trial study outcomes
 - **a.** Surgical complications such as infection, wound breakdown, readmission, reoperation, unplanned surgery, skin flap necrosis, implant loss, seroma, pain, capsular contracture and haematoma recorded at routine NHS clinic visits (or by nurse led telephone call or from hospital records) at 3- and 6-months post-surgery.

b. Patient reported outcomes (PROs) questionnaires: Breast Q and EQ-5D-5L completed at randomisation in the clinic or at home, 3- and 6-month post-surgery (postal or clinic).

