6.3. Enrollment and Randomisation Procedure

Before randomising a participant, written informed consent must have been obtained and confirmation of trial eligibility documented in the patient's medical notes. Following consent, participants will be enrolled and complete the baseline Breast Q and EQ-5D-5L questionnaires. They will be randomised to biologic matrix or synthetic mesh to allow sufficient days to order the allocated mesh for surgery. Participants will be blinded to the type of mesh (biological or synthetic mesh).

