6.5. Study assessments

6.5.1. Randomised participants

Participant demographics, medical history, and indication for surgery will be collected at randomisation. Operative details such as procedure time, placement of implant under or over the muscle, and hospital stay will be collected during the in-patient stay for surgery. Details of any treatment given after surgery will also be collected during follow-up. We are using validated questionnaires for participant reported outcomes that have been used previously.

Study Assessments	Baseline visit	Surgery admission	Month 3 post surgery	Month 6 post surgery
Consent	X			
Randomisation	Х			

Participant Demographics	X			
Medical History	X			
Indication for Surgery	X			
Operative Details		Х		
Post-Surgery Histology			Χ	
Post-Surgery Treatment Details				Х
Questionnaires (Breast Q, EQ-5D-5L) postal or clinic	Х		Х	Х
Follow-Up (Surgical Complications data collection; via clinic, telephone or hospital records)			Х	Х

Complications: such as infection, wound breakdown, readmission, reoperation, unplanned surgery, skin flap necrosis, implant loss, seroma, pain, capsular contracture and haematoma recorded at routine NHS clinic visits (or by nurse led telephone call or from hospital records) at 3 and 6 months post-surgery.

Patient reported outcomes (PROs) questionnaires: Patient-reported outcome data will also be collected in this feasibility study. We will assess aesthetic outcome and QoL with the widely used and validated reconstruction module of the Breast-Q questionnaire[11, 12]. This questionnaire has become the gold-standard measure of QoL for breast surgery, and was used in the National Mastectomy and Breast Reconstruction Audit[1]. It is comprised of independently functioning scales that measure outcomes and patient's experience of care (i.e. satisfaction with the surgeon, information and medical team). The QoL domain consists of three subdomains: physical, psychosocial and sexual wellbeing. The satisfaction with outcome domain also consists of three subdomains: satisfaction with breasts, satisfaction with overall outcome and satisfaction with care. A total Breast-Q score will be calculated (ranging from 0-100), with higher scores indicating greater satisfaction or better QoL. A minimum difference score of 4 points on the transformed 0 to 100 scale is clinically important when assessing an individual patient's outcome using the reconstruction module of the Breast-Q[13].

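### Section 3.1 needs the SD of the Breast-Q satisfaction-with-breasts score to size the main trial, but 6.5.1 names only a total score for calculation and 9.2 does not say which score it analyses

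*Protocol*

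**What the plan says.** - **Protocol 3.1 (Objectives)** fixes the planning input. The SD of the satisfaction-with-breasts "score on Breast Q questionnaire will inform sample size calculations for the main study". The same section makes that scale a main-trial outcome: "The follow-on main study will assess long-term (5 years) patient reported" satisfaction with breasts.
- **Protocol 3.2.2** lists the use of that input as a secondary outcome: "Sample size estimation: Estimate the sample size for the main study".
- **Protocol 6.5.1** says of the instrument: "It is comprised of independently functioning scales that measure outcomes". It lists satisfaction with breasts as one of several subdomains. On scoring it says: "A total Breast-Q score will be calculated (ranging from 0-100), with higher scores indicating greater satisfaction or better QoL". It states no other score calculation.
- **Protocol 9.2** says: "The standard deviation and effect size of Breast Q will be estimated using an Independent T-Test". No scale is named. It also says: "Secondary outcome measures will be presented overall and by study groups, as summary statistics at each assessment point".
- **Protocol 6.3 and 6.3.1** show what else is available. Before randomisation, "participants will be enrolled and complete the baseline Breast Q and EQ-5D-5L questionnaires", and allocation is stratified by site.

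**The concern.** The feasibility study is meant to hand one number to the designers of the main trial: the SD of a named scale. The section on scoring does not mention a score for that scale, and the section on analysis does not say which score it analyses. A statistician who follows 6.5.1 and 9.2 to the letter would compute a total and report its SD.

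A total over scales that the protocol itself calls independent is a different variable from any one of them, with a different SD. Because sample size is proportional to SD squared, a main trial planned on the wrong SD could be too small or too large for its own endpoint.

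A second, lesser matter is that baseline Breast-Q and site are both recorded but play no part in the between-arm estimate.

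**Working it through.** **1. The passages side by side**

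| Section | What it fixes | Score |
|---|---|---|
| 3.1 | SD used to size the main trial | Satisfaction with breasts |
| 6.5.1 | Score to be calculated | Total, 0-100 |
| 9.2 | SD and effect size | Breast Q, scale not named |

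Only 3.1 says which SD is used for sizing, and no section says that the total will be. The gap is that 6.5.1 and 9.2, as written, do not produce what 3.1 asks for.

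**2. The plan's own figures.** The protocol gives no SD, no between-scale correlation and no rule for forming the total, so there is no sizing figure to reproduce. The one figure used below is the 90% completion (54 of 60) in 9.1. Its stated interval of 80% to 95% reproduces with the Wilson method (79.9% to 95.3%).

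**3. Why the choice of score can matter (illustration on assumed inputs).** Suppose the total is the mean of k scales with equal SDs and common correlation r. Then SD(total)/SD(scale) = sqrt((1 + (k-1)r)/k), and the ratio of sample sizes is its square.
- k = 6, r = 0.3: sqrt(2.5/6) = 0.645; n ratio 0.417.
- k = 4, r = 0.7: sqrt(3.1/4) = 0.880; n ratio 0.775.

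If the other scales vary more than the named one, the direction can reverse. With SD 15 for the named scale, 20 for five others and r = 0.7:
- SD(total) = sqrt(0.3 × (15² + 5 × 20²) + 0.7 × 115²)/6 = sqrt(0.3 × 2225 + 0.7 × 13225)/6 = 16.60.
- n ratio = (16.60/15)² = 1.23.

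These assumptions therefore give anything from 42% to 123% of the n needed. This shows that the scale should be named. It does not measure an error in this trial.

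**4. Precision of the right SD.** With 54 completers in two arms there are 52 degrees of freedom. The 95% limits are sqrt(52/73.81) = 0.84 and sqrt(52/33.97) = 1.24 times the estimate, or 0.70 and 1.53 times on the n scale. This holds for any study of this size and is no defect, but it is a reason to report the SD with its interval.

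**5. The optional regression.** Inputs: 27 per arm, five sites (Study Summary), and an assumed baseline-to-follow-up correlation ρ. Half-widths are in SD units.
- t-test: t(52) × sqrt(2/27) = 2.0066 × 0.2722 = 0.546.
- Regression on arm, baseline and site has 54 - 7 = 47 df, so 5 of the 52 are used (one for baseline, four for site).
- With perfect balance: 2.0117 × 0.2722 × sqrt(1 - ρ²) = 0.548 (ρ = 0), 0.522 (ρ = 0.3), 0.438 (ρ = 0.6).
- Chance imbalance in baseline and site adds a little. Simulating 54 completers from 60, with five equal sites and blocks of 4 (both assumed), gives mean half-widths of about 0.556, 0.531 and 0.445 for the same three correlations.

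**The case against.** The strongest reply is that 3.1 already names the sizing variable. On that view 9.2 simply uses the questionnaire's name as shorthand. The end of the scoring sentence in 6.5.1 offers satisfaction or QoL as alternatives, which fits a 0-100 score per scale better than one grand total. The questionnaire is collected at every visit, so the satisfaction-with-breasts score can be derived whichever reading is right. Most of this stands. It limits the point to wording and makes it minor.

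It does not remove the point. Section 6.5.1 does not merely leave scoring to a later document. It states a rule, and that rule does not yield the variable that 3.1 requires. A SAP that followed it would inherit the mismatch.

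Two further objections hold in full. Whether the 3-month or the 6-month SD feeds the sizing is ordinary SAP detail, and its absence here is no defect. The unadjusted t-test is also legitimate: in a feasibility study of 60 women a descriptive comparison needs no covariates, and the unadjusted SD is a conservative planning value. A reader might infer from 9.2 that the analysis method is wrong, but the protocol does not support that.

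**Conclusion.** The point holds as a minor inconsistency: 3.1, 6.5.1 and 9.2 do not agree on which Breast-Q score supplies the planning SD.

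A reader might go further and conclude that the main trial will be sized on the total and so be underpowered. The documents do not support that. No passage commits to using the total for sizing, 3.1 still tells the main-trial designers which SD to use, and the direction of any error cannot be known without SDs, correlations and a scoring rule that the protocol does not give. The percentages above rest wholly on assumptions.

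The primary feasibility outcomes and the progression criteria in 9.4 do not depend on this SD. The regression is an improvement on offer, not the correction of an error, and its gain depends on an assumed correlation.

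**What to change.** **Wording (the point itself)**
- In 6.5.1, replace the total with a separate 0-100 score for each Breast-Q scale.
- In 9.2, state that the pooled within-arm SD of the satisfaction-with-breasts score, for example at 6 months, will be reported with its 95% CI and used to size the main study.

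No new data, visits or participants are needed.

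**Optional improvement**
- Estimate the between-arm difference by linear regression on arm, baseline score and site.
- Report the residual SD and the baseline-to-follow-up correlation, with 95% CIs, alongside the unadjusted SD. That correlation will be imprecise: with 54 completers, about 0.03 to 0.53 if the estimate is 0.3, and 0.39 to 0.75 if it is 0.6 (Fisher z, SE 1/sqrt(50)).
- Note that a 6-month correlation may not carry over to the 5-year outcome.

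The cost is about 5 of 52 residual degrees of freedom. If the covariates explained nothing, the half-width would rise from 0.546 to about 0.55-0.56 SD.

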9.3. Criteria for the Premature Termination of the Study

The Sponsor may suspend or prematurely terminate either the entire study, or the study at an individual site, for significant reasons that must be documented (e.g. an unacceptable risk to participants or serious repeated deviations from the protocol/ regulations). If this occurs the Sponsor shall justify its

decision in writing and will promptly inform any relevant parties (i.e. participants, investigators, participating sites, REC, regulatory bodies).

9.4. Progression criteria to main trial

The feasibility study will identify the challenges with study implementation and delivery. This will help us design the main trial that will measure women's satisfaction with reconstructed breasts, quality of life (QoL), complications and costs over 5 years. We will progress to writing the grant application for the main trial if ALL the criteria below are met:

- o Clinician acceptance (proportion of eligible women offered the trial) 50% and above
- o Patient acceptance (proportion of those offered the trial who consent & are randomised) 20% and above
- o Average recruitment rate, 30 per year (overall)
- o Compliance with allocated treatment (treatment acceptability) 80% and above

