Study Design:	A phase III feasibility randomised controlled trial in which
	participants will be randomised in a 1:1 ratio.
Study Participants:	Women undergoing mastectomy for breast cancer or risk
	reduction and immediate one-stage mesh assisted implant
	breast reconstruction as standard care.
Planner Number of Sites:	5
Planned Sample Size:	60 women (30 per arm)
Randomisation:	Participants will be randomised to biological matrix or synthetic
	mesh
Blinding:	Participants will be blinded to the type of mesh (biological or
	synthetic mesh).
Follow Up Duration:	6 months
Planned Recruitment Start	01 November 2023
Date:	
Planned Recruitment End Date:	30 November 2025
Planned Study End Date:	30 May 2026
Research Question/ Aims:	To assess patient and clinician acceptance, recruitment rate,
	compliance with randomly allocated type of mesh and data
	completeness.

FUNDING AND SUPPORT IN KIND

Funder(s)	Financial and Non-Financial Support Given
Derby & Burton Hospital's Charity (registered charity number 1061812).	Financial support
Consultant Oncoplastic Breast Surgeons and trainees	Surgeons and trainees participating in the study will undertake research activities.

Page 7 of 31 IRAS ID: 315581 BIOSYM Protocol v5 28/02/2025

ROLES & RESPONSIBILITIES

Sponsor

The Sponsor, University Hospitals of Derby & Burton NHS Foundation Trust, take on overall responsibility for appropriate arrangements being in place to set up, run and report the research project. The sponsor is not providing funds for this study but has taken on responsibility for ensuring finances are in place to support the research.

Funder

Derby & Burton Hospital's Charity (registered charity number 1061812). Feasibility study results will be used to apply for NIHR HTA funding for the main study.

Study Management Committees

Trial Management Group (TMG)

The TMG will meet regularly to oversee the day-to-day management of the trial, including all aspects of the conduct of the trial. Any problems with study conduct will be raised and addressed during TMG meetings.

The TMG will review recruitment, retention, compliance and data quality to ensure efficient trial conduct according to the research timeline. They will report to the independent Trial Steering Committee (TSC).

Trial Steering Committee (TSC)

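### Averaged over the full planned 25 months, the target of 60 women gives 28.8 per year against the required 30, and Section 9.2 wrongly treats this yearly rate as a proportion

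*Protocol*

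**What the plan says.** - **Threshold.** Protocol Section 9.4 lists "Average recruitment rate, 30 per year (overall" among the progression criteria and introduces the list with "We will progress to writing the grant application for the main trial if ALL the criteria below are met". No tolerance or intermediate zone is given.
- **Target.** The Study Summary plans "60 women (30 per arm", and Section 9.1 repeats "The sample size is 60".
- **Window.** The Study Summary gives "01 November 2023" as the planned start of recruitment and "30 November 2025" as the planned end.
- **Outcome.** Section 3.2.1 lists "Recruitment rate (average per year" as a primary outcome. Neither there nor in 9.4 does the protocol say when the time for the average starts and stops.
- **Analysis.** Section 9.2 says that "recruitment rate (average per year) will be presented overall as proportions along with 95% confidence intervals".
- **Replacement.** Section 6.6 provides for recruiting a replacement when a randomised woman is later found ineligible. Women who withdraw after randomisation are not replaced.

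**The concern.** The threshold, the target and the planned window are three figures that ought to fit together. The only recruitment period that the protocol states is 25 months, and 60 women spread over it fall just short of 30 per year. A trial that reached its target on the last planned day could therefore have met its recruitment plan and still be judged to have missed a mandatory criterion, depending only on how the average is formed. With a margin of one month, the choice of start and stop for the clock can decide the result. If that choice is made once the result is known, the outcome shapes the rule.

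The second matter concerns the same outcome. A yearly count has no binomial denominator, so an interval for a proportion does not apply to it. What is at stake is the clarity of a progression decision and the correctness of one reported interval. Neither matter affects any participant's treatment or biases the comparison of meshes.

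**Working it through.** **Inputs.** Target N = 60 (Study Summary; Section 9.1). Planned window 01 November 2023 to 30 November 2025 (Study Summary). Threshold 30 per year (Section 9.4).

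**1. Where 30 per year comes from.** 60 / (24/12) = 30.0 per year. The stated figure is reproduced by 60 women in 24 months, that is, by 31 October 2025 if the clock starts on the planned date.

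**2. Rate over the stated window.** The window is 761 days inclusive, or 25 calendar months.
- By months: 60 / (25/12) = 28.8 per year.
- By days: 60 / (761/365.25) = 28.8 per year.
- Shortfall: 30 − 28.8 = 1.2 per year, and 1.2/30 = 4%.

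**3. Reverse check.** 30 × 25/12 = 62.5 women over the full window. With whole women, 62/(25/12) = 29.8 and 63/(25/12) = 30.2, so 63 are needed, three more than the target.

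**4. What would meet the criterion as written.**
- 60 women within 24 months: 30.0 per year.
- 60 women by 30 November 2025 with a clock that starts one month after the planned date: 60/(24/12) = 30.0 per year.
- 63 women randomised over the full 25 months, for example through three replacements under Section 6.6: 30.2 per year.

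**5. Size of the gap against sampling error.** For a count of 60 in T = 25/12 years, the exact Poisson 95% limits of the count are χ²(0.025; 120 df)/2 = 45.8 and χ²(0.975; 122 df)/2 = 77.2. Divided by T, these are 22.0 and 37.1 per year. If recruitment instead stops at the 60th woman, so that the count is fixed and the time random, the upper limit uses 120 df: 76.1/T = 36.5, with the lower limit still 22.0. The threshold of 30 lies well inside either interval.

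**6. What one month is worth.** This step assumes constant Poisson recruitment at 28.8 per year, which the protocol does not state.
- Within 25 months the expected count is 28.8 × 25/12 = 60, and P(at least 60) = 0.517.
- Within 24 months the expected count is 28.8 × 2 = 57.6, and P(at least 60) = 0.393.

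**7. The wording in Section 9.2.** The same sentence covers clinician acceptance and patient acceptance, which are true proportions (women offered out of women eligible; women participating out of women offered). Recruitment per year is a count divided by time. It can exceed 1, and its uncertainty depends on the count and the time observed, not on a number of trials.

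**The case against.** A reader might infer that the trial is set up to fail its own criterion. The documents do not support that, for these reasons:

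- **A threshold may exceed the planned pace.** The dates are planned dates, and nothing says that the 60th woman is due on the last of them. Thirty per year for two years is 60 women, with one month of slack. This stands. It remains true that 9.4 gives no reason for a threshold above the pace that the full window needs. For patient acceptance the relation runs the other way: 50% is assumed in 9.1 and 20% is required in 9.4.
- **The time base is open.** The clock could start at first site opening or first randomisation and stop at the last randomisation. This stands, and it is why the shortfall is conditional. The detail may also be in a statistical analysis plan that is not shown, so its absence is not itself counted against the protocol. But threshold, target and dates are all fixed in the protocol, and on the one window stated there they do not agree.
- **The numerator may exceed 60** because of replacements under Section 6.6. This stands, although their number is unknown.
- **The wording is loose.** The other three criteria state explicitly that they are minima; this one does not. A minimum is still the natural reading.
- **The effect is slight.** Under the assumption in step 6, full alignment moves the chance of passing from 39% to 52%. Most of the risk comes from a hard threshold set near the expected rate, not from the extra month.
- **Late changes carry their own risk.** Protocol v5 is dated 28/02/2025, about 16 months into the planned window, and the Trial Management Group reviews recruitment. Lowering the threshold now could look post hoc. This stands and shapes the fix.
- **The word used in 9.2 is editorial.** Largely so, since the sentence itself says that the rate is an average per year. But it also prescribes the interval, and taken literally the interval would be wrong.

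**Conclusion.** The point holds in a conditional form. If the average is taken over the whole planned window and exactly 60 women are randomised, the rate is 28.8 per year, 1.2 (4%) below the mandatory 30. That is about one month of recruitment, or three women. It rests on two assumptions that the protocol does not fix: the full 25 months as denominator and exactly 60 as numerator. Change either slightly and the criterion is met. The gap is far smaller than the sampling error of the rate, so the stronger conclusion, that recruiting to plan must fail the progression rule, does not follow.

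The statement in Section 9.2 that a yearly rate is presented as a proportion is wrong as written, whatever time base is used.

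Together these make a low-end minor point. The arithmetic is certain; the practical consequence is small and conditional.

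**What to change.** **Section 9.4.** Before the recruitment result is assessed, and without reference to the observed rate:
- state the numerator (women randomised) and the start and end of the recruitment time used for the average;
- make the threshold of 30 per year, the target of 60 and the planned window agree on that basis, for example by stating that 30 per year corresponds to 60 women in 24 months;
- record the reason. Clarifying the definition is preferable to moving the threshold, which would be hard to defend this late in recruitment.

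**Section 9.2.** Take recruitment out of the list of proportions. Report it as women randomised divided by recruitment time, with a 95% confidence interval for a rate, for example exact Poisson.

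**Cost.** A few words in 9.4 and 9.2, and in the Study Summary if a date is changed, made through a documented amendment under Section 11.8. No extra data are collected and no participant is affected.
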